7.3. Variables

Source for all variables is the data lake of HDSF.

Table 2. List of study variables. Abbreviations: PO=primary objective, SO=secondary objective.

Variable	Role/Relevant objective	Operational definition
ICD-10 diagnoses; RCC diagnoses	Patient inclusion/exclusion IMDC risk category	yes/no
ICD-10 diagnoses: co-diagnoses (e.g. renal insufficiency and hypertension)	PO1, SO1	yes/no; co-diagnoses before and after index
Date of birth	Patient inclusion PO1	Date; age defined at index based on birth date
Date of death	End of follow-up PO3	Date
Gender	PO1	Female/male
Home municipality	Patient inclusion End of follow-up	Home municipality at each healthcare contact
Weight	PO1	kg
Height	PO1	m
Body mass index (BMI)	PO1	derived from weight and height
Smoking status (if available in structured format)	PO1	yes/no
Outpatient visits (including emergency room visits)	Patient inclusion and index definition (visits to oncologist) SO2	Date, physician's specialty, type of arrival
Hospitalizations	SO2	Start and end dates
Procedures and operations (including nephrectomy)	PO1 SO1 SO2	Procedure code, date
Medical imaging	SO1 SO2	Imaging code, date
Medications; including - hospital medications - prescriptions	Patient inclusion/exclusion and index definition PO2 PO3 SO1 SO2	Dates, ATC-codes, active substance
Laboratory testing	IMDC risk category PO1	Dates, test id, result
Zubrod/ECOG performance status	IMDC risk category PO1	scale 0-5; converted to Karnofsky
PAD histology (if available in structured format)	PO1	
Staging of RCC, the tumor-node-metastasis (TNM) classification	Patient inclusion and index definition PO1	scale 1-4 (stages)

PFIZER CONFIDENTIAL

Table 3. List of medications for RCC treatment. ATC= Anatomical Therapeutic Chemical.

	Active substance	Brand name	ATC-code at the moment in use	ATC-code previously in use
Oral medications	axitinib	Inlyta	L01EK01	L01XE17
	everolimus	Afinitor	L01EG02	L01XE10
	cabozantinib	Cabometyx	L01EX07	L01XE26
	pazopanib	Votrient	L01EX03	L01XE11
	sorafenib	Nexavar	L01EX02	L01XE05
	sunitinib	Sutent	L01EX01	L01XE04
Intravenous medications	ipilimumab	Yervoy	L01XC11	
	nivolumab	Opdivo	L01XC17	

7.4. Data sources

Cohort and data set formation overview is presented in Figure 2. The patient population will be selected from the health records at the data lake of HDSF based on diagnosis data and includes a personal identity code that is unique for every individual in Finland. For the identified RCC cohort, data of patient characteristics, diagnoses, healthcare contacts, treatments, laboratory and pathology tests, and performed procedures, operations and imagings will be collected from the same data lake of HDSF. The identification of the RCC cohort and collection of the additional data with personal identification numbers will be handled solely by the personnel of Auria Clinical Informatics. The identification codes are removed after linkage so that only pseudonymized data or group specific summary data is provided for analyses.

This study is conducted using existing and available clinical electronic records accessible from Auria Clinical Informatics. The study protocol and associated data request for all data will therefore be submitted to Auria Clinical Informatics for approval.

[figure not shown]

Figure 2. Overview of cohorts and data set formation.

7.5. Study size

The expected number of patients eligible for this study is approximated based on publicly available data from the Finnish Cancer registry (<https://syoparekisteri.fi/tilastot/tautitilastot/>):

- In HDSF, there have been approximately 1,100 RCC patients during 2010-2021.
- 20-50% of RCC patients develop advanced/metastatic disease [9] and therefore, the size of mRCC-patient cohort is approximately 220-550 patients.

7.6. Data management

All data collection, storage and handling will be coordinated by Auria Clinical Informatics. Auria Clinical Informatics collects the required data, pseudonymizes the IDs and releases the row level pseudonymized data to a secure analysis environment maintained by Auria Clinical

Informatics. All data-analyses will be performed by the Medaffcon Oy analytics team in the secure analysis environment using the statistical software R (version 3.6.1. or higher). No patient level data will be transferred outside of this system. Only aggregate level and/or fully anonymous data and/or summary statistics may be transferred outside this system for reporting and publication purposes. Thus, individual patients cannot be identified from this data set.

7.7. Data analysis

Data will be analyzed using primarily descriptive measures, which include mean/median values for continuous variables and proportions for categorical variables. Costs will be estimated using data of visits, hospitalizations, procedures, etc. and utilizing publicly available price listings. For treatment outcomes, Kaplan-Meier estimates and/or corresponding time to event competing risk models will be utilized.

All analyses will be reported for the whole advanced/metastatic RCC patient population and stratified by the IMDC risk score. Additionally, treatment patterns and treatment outcomes will be reported by treatment lines.

Analyses are based on structured data, with the exception for potential text-mining of IMDC risk score or its components.

Due to the retrospective nature of the study, missing and/or incomplete data is expected in some of the medical records. Patients' records will not be excluded because of missing values, and missing data will not be imputed, i.e. the data will be analyzed as they are recorded in the electronic medical records. The proportion of missing values per variable will be reported.

Analyses will be performed using R, a language and environment for statistical computing, in Rstudio-server environment.

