NON-INTERVENTIONAL (NI) STUDY PROTOCOL

Study information

Title	Registry-based non-interventional analysis of advanced/metastatic renal carcinoma treatment patterns and outcomes in the Hospital district of Southwest Finland.
Protocol number	A4061098
Protocol version identifier	Version 1
Date	28 March 2022
Active substance	axitinib, ATC-code L01EK01 (previously L01XE17) sunitinib, ATC-code L01EX01 (previously L01XE04)
Medicinal product	Inlyta; Sutent
Research question and objectives	The aim of the study is to describe the characteristics, treatment pattern and outcomes of patients with advanced/metastatic renal cell carcinoma (RCC) with medical records in the HDSF data lake. The treatment sequence of mRCC patients and treatment outcomes (overall survival, time-to-next treatment) will be analysed with regard to individual risk score of the patient and over time. In addition, comorbidities, procedures and healthcare usage will be analyzed. As an exploratory objective, the coding practices especially with regard to risk score calculation are assessed.
Author	PPD [REDACTED], PhD, PPD [REDACTED] [REDACTED] email: PPD [REDACTED] tel. PPD [REDACTED]

PFIZER CONFIDENTIAL

[REDACTED]

TABLE OF CONTENTS

1. TABLE OF CONTENTS.....	2
2. LIST OF ABBREVIATIONS.....	4
3. RESPONSIBLE PARTIES	5
4. AMENDMENTS AND UPDATES.....	6
5. MILESTONES.....	7
6. RATIONALE AND BACKGROUND.....	7
7. RESEARCH QUESTION AND OBJECTIVES	9
7.1. Primary objectives	9
7.2. Secondary objectives.....	9
7.3. Exploratory objective	10
8. RESEARCH METHODS	11
8.1. Study design	11
8.2. Setting.....	11
8.2.1. Inclusion criteria	12
8.2.2. Exclusion criteria	13
8.2.3. Patient stratification	13
8.3. Variables.....	14
8.4. Data sources	16
8.5. Study size	17
8.6. Data management	17
8.7. Data analysis	18
8.7.1. Patient characteristics	18
8.7.2. Treatment patterns and treatment lines.....	19
8.7.3. Treatment outcomes.....	20
8.7.4. Morbidity	21
8.7.5. Healthcare resource utilization	21
8.7.6. Changes in coding practices over time	22
8.8. Quality control.....	22
8.9. Limitations of the research methods	22
8.10. Other aspects	23

9. PROTECTION OF HUMAN SUBJECTS	23
9.1. Patient information	23
9.2. Patient consent	23
9.3. Institutional review board (IRB)/Independent ethics committee (IEC)	23
9.4. Ethical conduct of the study	23
10. MANAGEMENT AND REPORTING OF ADVERSE EVENTS/ADVERSE REACTIONS	23
11. PLANS FOR DISSEMINATING AND COMMUNICATING STUDY RESULTS.....	24
12. REFERENCES	24
13. LIST OF TABLES	25

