5. RATIONALE AND BACKGROUND

Renal cell carcinoma (RCC) is among the 10 most frequently occurring cancers and the most common type of kidney cancer occurring in Western communities [1]. RCCs comprise a heterogeneous group of malignant neoplasms arising from the nephron. Risk factors for RCC include obesity, hypertension, cigarette smoking, diet, diabetes, and male gender [1].

After decades of increasing trends in RCC incidence and mortality rates, it seems that rates are stabilising or starting to decline in many Western countries [1]. The worldwide number of kidney cancer cases was 431,288 (62.9% male) and deaths 179,368 (64.4% male) in 2020 [2]. Kidney cancer is more common in males compared to females. The incidence was 7.8 and mortality 3.0 per 100,000 males in high human development index countries in 2020 [2]. In Finland, the number of new kidney cancer cases was 635 in males and 353 in females in 2019 [3], and the number of prevalent patients was 4,943 males and 3,867 females in 2019 according to the Finnish Cancer Registry [4].

Localized RCC can be curatively treated with nephrectomy. However, about 20–30% of patients present with metastatic RCC (mRCC) at the time of diagnosis [5]. In addition, another 20% of patients with localized RCC undergoing nephrectomy will have a relapse and develop mRCC during follow-up. Despite the recent advances in mRCC treatment, metastatic disease is often fatal [6].

[figure not shown]
Over the last decade, the treatment of advanced/metastatic RCC has been constantly evolving, especially in the last 2-3 years with the emergence of several novel treatment options in rapid succession. Current recommendations for first-line therapy of mRCC include several combination treatments, superseding the previously recommended antiangiogenic agent monotherapies. The novel options combine an anti-PD-1-antibody with either an antiangiogenic drug (vascular endothelial growth factor receptor (VEGFR) tyrosine kinase inhibitor (TKI)), or an anti-CTLA-4-antibody. The combination treatments are recommended

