7.2.3. Patient stratification

Analyses will be stratified by:

- IMDC risk category (defined at the initiation of the first treatment for the metastatic RCC; see Table 1 and listing below for definitions)
 - Applied to all primary and secondary objectives
- Treatment line
 - Applied to primary objective 2 and 3

IMDC risk factors (each criterion accounts for +1 for the risk score):

1. Less than a year from time of initial RCC diagnosis to initiation of treatment for the metastatic RCC

2. Performance status* <80% (Karnofsky)
3. Hemoglobin* below normal (women < 117 g/l; men < 134 g/l)
4. Serum calcium* above normal (> 2.51 mmol/l)
5. Neutrophiles* above normal (> 6.3 x 10⁹/l)
6. Thrombocytes* above normal (> 350 x 10⁹/l)

** for performance status and laboratory values data of ± 3 months around the treatment initiation will be utilized due to possibly sparse data. If multiple records are available, the record closest to the treatment initiation will be utilized.*

Table 1. IMDC risk scores and categories based on two different approaches depending on the data coverage

	IMDC risk category	Total score of IMDC risk factors	Explanations/missing values
Option 1*	Favorable risk	0	no missing values allowed
	Intermediate risk	1-2	1) total score = 1; max 1 risk factor allowed to have missing value 2) total score = 2; no missing values allowed
	Poor risk	3 or more	max 3 risk factors allowed to have missing values
	Unknown risk**	-	when none of the above risk categories can be assigned
Option 2*	Appear favorable	0	all non-missing values for the risk factors indicate favorable risk max 3 risk factors allowed to have missing values
	At least intermediate	≥1	at least one risk factor criterion is met max 3 risk factors allowed to have missing values
	Poor	≥3	at least three risk factor criteria is met max 3 risk factors allowed to have missing values
	Unknown**	-	when none of the above risk categories can be assigned, i.e. more than 3 risk factors have missing value

** If small number of missing values is observed, the option 1 will be selected. If large number of missing values is observed and thus majority of patients were to belong to the “unknown” group of the option 1, the option 2 will be selected. The selection will be done after the data release and monitoring of data coverage.*

*** Patients with unknown risk category, will be analysed as own patient group.*

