7.7.2. Treatment patterns and treatment lines

Primary objective 2:

The treatment lines will be defined using drug administration and prescription data. The treatment options and lines will be visualized using Sankey plots and the proportion of patients per treatment type will be reported.

In general in mRCC, line of treatment (LOT) changes when the active substance changes, as the treatments are mainly monotherapies and only a few options consist of two substances (e.g. combination of ipilimumab and nivolumab in 1L).

The treatment lines will be defined *post hoc* using following process:

- For each active substance, single administrations/prescriptions are merged to treatment continuums.
- To identify, whether the treatment is monotherapy or combination of two active substances, the first records of the active substances will be considered

- if the first records of the two active substances are within 28 days, the treatment is considered as combination therapy of these two medications
- otherwise the two active substances are considered as two separate treatment lines
- The initiation of the treatment line is defined as the date of first record (dosing or prescription) of the active substance.

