7.7.3. Treatment outcomes

Primary objective 3:

The treatment outcomes will be assessed using time-to-event analysis, namely Kaplan-Meier fit or other relevant competing risk models. For each outcome, the time will be defined as follows (Figure 3):

- overall survival:
 - time from index until death (event) or end of study (censoring event)
 - when analysing by treatment lines, start the time from initiation of each treatment line
- progression free survival (PFS, defined using time to next treatment (TTNT) proxy):
 - time from initiation of the current treatment line until the initiation of the next treatment line (event), death (competing risk/event), or end of study (censoring event)

The Kaplan-Meier fits will be visualized, and the median survival/PFS of the patients will be reported as well, if reached.

Additionally, corresponding Cox proportional-hazards model will be fitted, including clinical variables as covariates (including but not limited to age, sex, IMDC risk score, diagnosis year, and treatment line number). The hazard ratios, 95% confidence intervals and p-values corresponding to each covariate will be reported.

[figure not shown]

Figure 3. Graphical illustration of definitions of treatment outcomes. Abbreviations: LOT = line of treatment.

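### Treatment sequence has no calendar-time analysis, and outcomes have only a diagnosis-year Cox covariate, although the research question promises both over time

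*Combined protocol and SAP*

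**What the plan says.** **The promise.** The research question in the Study information table says that treatment sequence, overall survival and time to next treatment "will be analysed with regard to individual risk score of the patient and over time". Section 5 shows why calendar time matters. It says that treatment has kept changing, "especially in the last 2-3 years with the emergence of several novel treatment options in rapid succession".

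**The strata.** Section 7.7 states: "All analyses will be reported for the whole advanced/metastatic RCC patient population and stratified by the IMDC risk score". It then adds: "Additionally, treatment patterns and treatment outcomes will be reported by treatment lines". Section 7.2.3 lists the same two stratifiers. IMDC category covers all primary and secondary objectives, and treatment line is "Applied to primary objective 2 and 3". No calendar period is listed.

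**Treatment patterns (7.7.2).** "The treatment options and lines will be visualized using Sankey plots and the proportion of patients per treatment type will be reported". Nothing is split by year or period.

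**Outcomes (7.7.3).** Kaplan-Meier curves and medians are planned without a period split. The Cox model has clinical covariates "including but not limited to age, sex, IMDC risk score, diagnosis year, and treatment line number", and "The hazard ratios, 95% confidence intervals and p-values corresponding to each covariate will be reported".

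**The concern.** The metastatic cohort is entered from 1 January 2010 to 31 December 2021, which is 12 calendar years. If treatment changed within that window, one Sankey plot or one set of drug shares is an average over different treatment eras and need not describe practice in any of them. A reader could not see from it when a drug came into use or left first line, which is what an analysis of treatment sequence over time should show.

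For outcomes, the diagnosis-year covariate gives some information on calendar time, but not enough for a study that is mainly descriptive:

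- One hazard ratio gives no survival curve or median for any period.
- The form of the term (linear or categorical) is not stated.
- The text does not say whether the year is that of the first RCC diagnosis or of the metastatic diagnosis. Section 7.2.2 keeps patients with local disease before 2010 who metastasise later, so under the first reading the year can lie before the study window.
- For second and later lines, the drugs on offer depend on when that line began, and diagnosis year does not record this.

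**Working it through.** **1. Calendar-time elements, section by section.**

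| Analysis | Calendar-time element |
|---|---|
| Stratifiers (7.2.3, 7.7) | none |
| Treatment patterns, primary objective 2 (7.7.2) | none |
| Kaplan-Meier curves and medians, primary objective 3 (7.7.3) | none |
| Cox model, primary objective 3 (7.7.3) | diagnosis year, with hazard ratio, confidence interval and p-value |
| Resource use (7.7.5) | none; year since index is not calendar time |
| Coding practices, exploratory (7.7.6) | year of metastatic diagnosis |

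The gap is complete for treatment sequence and partial for outcomes.

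**2. Is a period split feasible?** Section 7.5 gives about 1,100 RCC patients, of whom 20-50% become metastatic: 1,100 × 0.20 = 220 and 1,100 × 0.50 = 550. This reproduces the plan's 220-550. The treated share is not given. Assuming 50-100%, the treated cohort is 110 (220 × 0.5) to 550 (550 × 1.0). Assuming equal-sized groups:

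- Two periods: 110/2 = 55 to 550/2 = 275 patients each.
- Three periods: 110/3 ≈ 37 to 550/3 ≈ 183 each. The 95% half-width for a share of 50% is 1.96 × √(0.25/n), or about 16 points at n = 37 and 7 points at n = 183.
- Three periods by four IMDC groups: 110/12 ≈ 9 to 550/12 ≈ 46 per cell.

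Periods alone are workable at first line. Periods by IMDC category are thin at the low end, and later lines will be smaller still.

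**3. Does pooling distort the Kaplan-Meier estimate?** The documents give no survival figures, so this is an illustration. Assume uniform entry over 12 years, exponential survival, a change of median after year 8, and administrative censoring at year 12. With rates λ = ln 2/median, the numbers at risk at t years (t ≤ 5) are proportional to min(8, 12 − t)·exp(−λ₁t) for early entrants and max(0, 4 − t)·exp(−λ₂t) for late entrants. The pooled hazard is the average of λ₁ and λ₂ with these weights, and the pooled curve is exp(−its integral). The true mixture is [8·exp(−λ₁t) + 4·exp(−λ₂t)]/12.

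| Medians, early/late (months) | Pooled median | Mixture median | Pooled 5-year | Mixture 5-year |
|---|---|---|---|---|
| 18/36 | 21.4 | 22.3 | 12.5% | 17.1% |
| 20/30 | 22.2 | 22.8 | 14.1% | 16.7% |
| 24/24 | 24.0 | 24.0 | 17.7% | 17.7% |

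The mixture value at five years in the first row is (8 × 0.099 + 4 × 0.315)/12 = 0.171. The tail is pulled down because late entrants cannot be followed beyond four years. The median moves by less than one month, and with no change between eras there is no effect.

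**The case against.** **The promise is thin.** The phrase stands only in the Study information table and is not defined. Primary objectives 2 and 3 in section 6.1 state no calendar-time aim, and the protocol elsewhere uses the same phrase for time since diagnosis (resource use, section 6.2). This stands in part, since one clarifying sentence could settle the meaning. But section 6.2 adds that the clock runs from diagnosis, section 6.3 uses the phrase for coding changes that are analysed by calendar year, and section 5 stresses recent change. Calendar time is the natural reading.

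**Outcomes are analysed by calendar time.** This stands as far as it goes. A reader might infer that no outcome analysis uses calendar time, and that every analysis is split only by IMDC category and line. The documents do not support that: the Cox model reports a hazard ratio for diagnosis year, and coding practices are reported by year. The covariate list is also open-ended, so year of line start is not excluded. It is simply not planned.

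**The size of any local change in treatment is unknown.** This stands. Section 5 describes general recommendations and says that Finnish reimbursement makes combinations difficult. Section 7.7.2 expects mainly monotherapies. That leaves open how much changed in this district, which a period split would show.

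**The cut-points are arbitrary and the cells small.** Also fair. It argues for few periods, fixed in advance, without further splitting.

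**Conclusion.** The point holds as a mismatch between the research question and two of the three primary objectives. It is complete for treatment sequence and partial for outcomes. It should be corrected, but it does not invalidate the planned analyses. It rests on reading the phrase in the research question as calendar time.

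A reader might go further and infer that the pooled Kaplan-Meier results are seriously biased. The documents do not support that. The era medians and the change point in the illustration are assumed, and section 7.7.3 plans curves and a median but names no five-year estimate. The median is off by about 0.8 months (18/36) or 0.5 months (20/30). With 220 treated patients, itself an assumption, the 95% sampling range of the first median is about 17.6-26.0 months, far wider than the shift. Nor are all late entrants censored early: with a 36-month median and follow-up uniform over 0-4 years, the share who die under observation is 1 − (1 − e^(−0.924))/0.924 ≈ 35%, where 0.924 = 4 × ln 2/3. The effect on the tail is a secondary reason for showing periods separately.

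**What to change.** - **7.2.3:** add calendar period of line start as a stratifier for primary objectives 2 and 3. Use two or three periods, with cut-points fixed before outcomes are analysed. For survival from the metastatic index date, use the period of that date.
- **7.7.2:** report drug shares per line by period of line start, and Sankey plots by period. A Sankey plot follows patients across lines, so group it by start of first line and note that recent starters have had less time to reach later lines.
- **7.7.3:** report overall survival and time to next treatment by period, showing each curve only over the follow-up available in that period. In by-line Cox models use year of line start, and state the form of the term. Where diagnosis year is kept, say which diagnosis is meant.
- **Study information and section 6:** state that the phrase means calendar time. If another meaning is intended, amend the research question instead.

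The cost is a few more tables and curves. No new data are needed, because section 7.7.2 already derives the start date of each line. Some cells will be small, so show periods without IMDC sub-splits and combine periods where a later line has few patients.
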